To explore the best ways of minimising repetition within the HOME core outcome set, we will be using an existing eczema trial dataset to evaluate whether the responses to the identical questions from the two questionnaires called: POEM and RECAP are similar enough to only ask once. We will also compare the agreement within the 'frequency of itch' questions and 'intensity of itch' questions from different questionnaires to assess whether they add value to the core outcome set.

The results of this project will fill an important gap in our understanding of how to best collect the HOME core outcome set. In addition, this work will help to minimise the burden of using the HOME core outcome set and thus can potentially improve uptake. This will provide a better evidence base for patient care.

Study synopsis

Title	Assessing the redundancy of itch assessments in the HOME	
	core outcome set for eczema clinical trials	
Aims & objectives	Aim: To explore the relationship between the different itch questions contained in the HOME core outcome set and understand the implications for implementation of the core set. Objectives: • To assess the level of agreement between the POEM and RECAP 'frequency of itch' questions (Note: these questions are identical but administered within the context of different questionnaires) • To explore the impact of using the 'first collected answer' to the frequency of itch question on the EMO trial results. • To assess the correlation between all available itch measurements: • Frequency of itch (POEM and RECAP) • Intensity of itch (RECAP and NRS itch)	
Study Design	Secondary data analysis, using existing data collected in a previously completed online trial (EMO). Ethics approval was granted for the EMO trial. This study does not require ethical approval.	
Research questions	Research question 1: Are the identical questions included in the POEM and RECAP questionnaires (frequency of itch) sufficiently similar to enable collection only once? Research question 2: Is there redundancy in the HOME core outcome set itch questions or do they all add value?	
Eligibility (data source)	EMO trial dataset accessible from: https://rdmc.nottingham.ac.uk/handle/internal/10456	
Outcomes	This work will help to minimise the burden of using the HOME core outcome set and thus improve uptake which will in turn provide better evidence base for patient care. The results of this project will fill some of the gaps in our understanding of how to best collect the HOME core outcome set.	
Sample size	296 participants in the EMO randomised controlled trial. Self-completed data with available measurements for RECAP, POEM and NRS Itch will be used in this project.	
Analysis	 Exploratory analysis using descriptive statistics (analysed using STATA version 18) Levels of agreement calculated using weighted kappa and kappa statistic. Correlations reported using Pearson's correlation 	

Background

What is eczema?

Eczema is a chronic, inflammatory skin condition characterised by itchiness and dry skin (Weidinger and Novak, 2016). It affects 1 in 5 children and 1 in 10 adults (Association, 2023). There are remitting and relapsing cycles with eczema, also known as flare-ups. During flare-ups, people can experience severe itching, weeping, swelling and bleeding (NHS, 2019). In eczema, the skin barrier (epidermis) is compromised, allowing moisture to leave the skin making it prone to allergens entering through the epidermis. Despite it being such a common condition, the cause is still not fully understood but it is thought to be a complex interplay of genetic and environmental factors, such as genetic predisposition, stress, dust, temperature extremes and wash products. People can experience mild, moderate, or severe eczema but all severities have a significant impact on quality of life affecting self-confidence and causing sleeplessness, anxiety, and depression. It is important to consider the itching associated with eczema can be intense, which does exacerbate the symptoms of eczema in many people.

Treatments for eczema can ease symptoms, but there is no cure. The mainstay of eczema treatments are emollients and topical corticosteroids (NICE, 2023). Alternatively, reducing scratching by wearing gloves or keeping short nails and avoiding triggers for flare-ups as preventative measures (NHS, 2019). Itching is the main symptom and an essential criterion for diagnosis of eczema according to the UK Diagnostic Criteria for Eczema ((NICE), 2023)

Core outcome sets

Core outcome sets (COS) are a consensus-based set of outcomes that should be measured and reported in all clinical trials for a particular disease (Williamson et al., 2012). Core outcomes are not restrictive but are the expected minimum outcomes that should be reported in all the clinical trials of a certain condition. The Core Outcome Measures in Effectiveness Trials (COMET) Initiative was established to overcome the issue of outcome heterogeneity, which makes it difficult to compare results from several trials about the same condition. The COMET initiative promotes COS development, by bringing researchers, the public and methodologists together and collate ideas and combine to form COS for certain conditions (COMET, 2023). Measuring the same set of outcomes allows study results to be combined in systematic reviews and meta-analyses (Williamson et al., 2012). They improve the quality of evidence-based knowledge, so it is more useful to make clinical decisions and reducing research waste. Without COSs, important outcomes will not be investigated, which could exclude many participants who have given their time to contribute to research (Williams et al., 2022).

HOME Initiative Core Outcomes

The Harmonising Outcomes Measures for Eczema (HOME) initiative have created a COS minimum that should be measured in all eczema clinical trials. In the past, there have been a lot of unvalidated outcome measures for eczema which leads to clinical trials being incomparable, inconsistent and

failure to come up with an effective intervention (Charman et al., 2003). The core outcome sets ensure there is a standardised framework to assess the effectiveness of interventions of eczema. The HOME initiative focuses on four outcome measures: clinical signs, patient-reported symptoms, long-term control, and quality of life (Williams et al., 2022). For clinical signs, the Eczema Area and Severity Index (EASI) is used (Hanifin et al., 2001). It is a scoring system used by clinicians for grading physical signs of eczema. The patient-reported symptoms core domain includes the Patient-Oriented Eczema Measure (POEM) instrument (Charman et al., 2004) that measures eczema symptoms from the patient perspective and the Numerical Rating Scale (NRS) 11-point measures for itch intensity over last 24 hours. The quality-of-life outcome domain contains three questionnaires for different age groups: the Dermatology Life Quality Index (DLQI) for individuals aged 16 years and above (Finlay and Khan, 1994), the Children DLQI (CDLQI) for children aged 4 to 15 years (Lewis-Jones and Finlay, 1995) and Infant DLQI (IDQoL) for the age 4 and below (Lewis-Jones et al., 2001). For the long-term control domain, the RECAP of Atopic Eczema (RECAP) (Howells et al., 2020) and Atopic Dermatitis Control Tool (ADCT) instruments are used to assess eczema control (Simpson et al., 2019).

Challenge of Implementing COS

A COS is only useful if it is used and widely implemented. The insufficient uptake of a COS is a common problem across most trials. The main reasons for the limited uptake of the HOME COS might be due to the lack of stakeholder awareness and engagement, universal applicability, and the administrative burden associated with its use (Leshem et al., 2023). Once a COS has been established, it can be many years before the full benefits are realised and it requires all stakeholders to be aware and supportive. It is important to involve the main stakeholder in COS development to form a credible COS. Involving stakeholders in decisions has proven an increase in uptake of HOME COS by the research community (Vincent et al., 2020). The HOME initiative includes members of the public, clinicians, methodologists, researchers, regulator. To ensure there is also continued global intake, consensus meetings should be held in countries around the world to inform the results and updates of these COS. The HOME stakeholders suggest there should be a maximum of four outcome measures to make it accessible to participants. Other ways to make sure COS is easy to use on a large scale is the time to complete the COS, avoiding overlapping questions, the cost, and the availability of instruments. The uptake will also improve if you decrease uncertainty in the COS. It is recommended that each COS should make it clear how to measure and report each outcome using which instruments. The HOME initiative, for example, published on how to report answers from the EASI and POEM questionnaires in a standardised way (Leshem et al., 2023).

This project will focus on how HOME can reduce burden for participants by assessing the effect of the overlapping questions contained in the COS.

Itch Questions in HOME COS

Questions about itch is assessed five times by four patient-reported instruments in the HOME COS (POEM, RECAP, NRS Itch, DLQI). Some of the itch questions are overlapping. Each scale was developed and validated separately, so it is not possible to simply remove overlapping questions. This could mean unnecessary responder burden, meaning participants could find partaking time-consuming, stressful, and difficult (Williams et al., 2022). This questions the feasibility of the HOME COS which in turn affects implementation. The 'frequency of itch' and 'intensity of itch' questions are repeated in individual questionnaires. Questions about the patient's frequency of itch is asked

three times within the COS by POEM, RECAP and in the three variations of DLQI. The questions about patient's itch intensity are asked twice in the HOME COS by RECAP and the NRS itch questionnaire. While some repetition can be useful to ensure the consistency of responses, excessive repetitions of a question can reduce the accuracy of the data collected due to the burden on participants. There needs to be a balance between collecting the necessary data to analyse and respecting the participant's time and effort. Based on the results, recommendations will be made to HOME on how to best collect data about patient-reported itch.

Filling Validation Gaps

This project will explore whether all itch questions are required to be included in the HOME COS. This will be the first step to inform future HOME consensus discussions on this topic. If avoidable redundancy is identified, this could help the uptake of the COS by minimising the burden of data collection when using the HOME COS (Williams et al., 2022).

This will be done by exploring the relationship between the responses of the itch questions from different questionnaires, using various statistical methods. This project is a secondary data analysis project using the Eczema Monitoring Online (EMO) trial dataset. The EMO dataset includes data from the RECAP, POEM, and NRS-11 questionnaires. Since the EMO trial did not assess the quality of life the itch questions from the quality-of-life instruments will not be assessed in this project.

Methods

Aim:

To explore the relationship between the different itch questions contained in the HOME core outcome set and understand the implications for implementation of the core set.

Research question 1:

Are the identical questions included in the POEM and RECAP questionnaires (frequency of itch) sufficiently similar to enable collection only once?

Research question 2:

Is there redundancy in the HOME core outcome set itch questions or do they all add value?

Study design

This will be a secondary data analysis project using existing data collected in a previously conducted online trial (EMO). Ethical approval for the EMO trial was obtained from the University of Nottingham Research Ethics Committee (reference number: 239-0421). This study does not require ethical approval because it uses the already existing EMO dataset for secondary analysis.

Data sources

Eczema Monitoring Online (EMO) trial dataset is accessible from https://rdmc.nottingham.ac.uk/handle/internal/10456. The dataset contains patient-reported outcome assessments collected at baseline and week 8, assessed by the EMO trial dataset includes a

total of four itch questions from POEM, RECAP and NRS Itch as shown in Table 1. The DLQI is not part of the database so it will not be included.

Table 1. Itch questions available in the EMO trial dataset

Questionnaire	Question	Frequency or Intensity
RECAP	Over the last week, on how many days has your skin been itchy because of your eczema?	Frequency
POEM	Over the last week, on how many days has your skin been itchy because of the eczema?	Frequency
RECAP	Over the last week, on how many days has your skin been intensely itchy because of your eczema?	Intensity
NRS Itch	On a scale of 0 to 10, with 0 being 'no itch' and 10 being 'worst itch imaginable', how would you rate your itch at the worst moment during the previous 24 hours?	Intensity

The kappa and correlation will only use the data from baseline (not week 8 after the intervention) The main variables that will be investigated from the database are the POEM frequency of itch, RECAP frequency of itch, RECAP intensity of itch, NRS intensity of itch questions. The variables used will also include all questions from baseline and follow-up in POEM and all baseline questions in RECAP (see Appendix).

Statistical analysis and sample size

Analysis methods

This is an exploratory secondary project and is not formally testing a hypothesis. Analyses will use STATA (version 18) and will focus on descriptive statistics. Statistics will be presented with 95% confidence intervals (CI) where appropriate.

Objective 1: To assess the level of agreement between the POEM and RECAP 'frequency of itch' questions

Levels of agreement between the identically worded frequency of itch questions in the POEM and RECAP will be evaluated using both a weighted kappa (primary method) and kappa.

The itch question is an ordinal scale from 0 to 4 (ranging from no days to every day). Kappa weightings will be applied using a quadratic approach as follows (Sim and Wright, 2005):

- Difference of 0 between the POEM and RECAP questions = 1.00
- Difference of 1 between the POEM and RECAP questions = 0.89
- Difference of 2 between the POEM and RECAP questions = 0.56
- Difference of 3+ between the POEM and RECAP questions = 0.00

A high level of agreement (suggesting that the item may not need to be asked twice) is defined as being a correlation \geq 0.8.

Objective 2: To explore the impact of using the 'first collected answer' to the frequency of itch question on the EMO trial results.

For the analysis exploring impact on the EMO trial results, the original syntax from the trial analysis will be used. The trial results will be re-calculated using the total POEM scores at baseline and week 8, which have been calculated in two ways:

- Using the original POEM scores (7-items, range from 0 to 28)
- Using 6 items from the original POEM score, plus the frequency of itch question from the RECAP outcome instrument (7 items, range 0 to 28)

Trial results will be presented with mean between group difference and 95% CIs to explore the likely impact on the trial conclusions of collecting the frequency of itch questions only once.

Objective 3: To assess the correlation between all available itch measurements:

The association between frequency of itch questions (POEM and RECAP) and intensity of itch questions (RECAP and NRS-itch) will be explored using Pearson's correlation coefficients and 95% confidence intervals.

A high level of agreement (suggesting that the item may not need to be asked twice) is defined as being a correlation \geq 0.8.

Results of this project will help provide the evidence for HOME to resolve any uncertainties in the assessment of itch in the current COS. In turn, this will improve the accuracy and feasibility of the HOME COS and help to enhance its uptake.

Sample size

The sample size was determined by the availability of required data in the EMO trial.

Consensus-based Standards for the selection of health Measurement Instruments (COSMIN) helps researchers evaluate the psychometric properties of outcome measurement instruments. For studies assessing construct validity, COSMIN recommends that a sample size of over 100 is appropriate to use (Prinsen et al., 2016); the EMO trial has a sample size of >200. Only data from self-completers will be used, data from parents of children will be excluded due to the low number of participants (n = 15).

Patient and Public Involvement

This research project will be utilising a secondary dataset, so there will be no direct patient and public involvement (PPI). However, in the EMO trial dataset six members of the entre of Evidence Based Dermatology Patient Panel were involved in the design of the secondary outcome measures. The PPI members also provided feedback on the patient facing materials, including participant information sheet, consent form and social media adverts for recruitment.

Study Management

I will be the project manager for this dissertation under the supervision of [name], [name], and [name]. Under the University of Nottingham policy, we are required to store research data securely. The data will be stored in our restricted access Microsoft Teams file, where it will only be accessible to the people assisting in this project.

Publication and dissemination

This project is a part of my BMedSci. Following completion, I will be required to create a poster and present it twice. There is potential for publishing in a peer reviewed journal. The results will be presented at the next HOME meeting and be used to inform consensus recommendations around the bast ways of using the HOME core outcome set.

References

- (NICE), N. I. F. H. A. C. E. 2023. *Atopic Eczema Diagnosis* [Online]. Available: https://cks.nice.org.uk/topics/eczema-atopic/diagnosis/diagnosis/ [Accessed 29 October 2023].
- ASSOCIATION, N. E. 2023. Eczema Stats [Online]. Available:

 https://nationaleczema.org/research/eczema-facts/#:~:text=It%20is%20estimated%20that%201,prevalence%20peaking%20in%20early%2
 Ochildhood. [Accessed 29 October 2023].
- CHARMAN, C. R., VENN, A. J. & WILLIAMS, H. C. 2004. The Patient-Oriented Eczema Measure:

 Development and Initial Validation of a New Tool for Measuring Atopic Eczema Severity
 From the Patients' Perspective. *Archives of Dermatology*, 140, 1513-1519.
- COMET. 2023. *COMET Initiative | Home* [Online]. Available: https://www.comet-initiative.org/ [Accessed 2 November 2023].
- FINLAY, A. Y. & KHAN, G. K. 1994. Dermatology Life Quality Index (DLQI)--a simple practical measure for routine clinical use. *Clin Exp Dermatol*, 19, 210-6.

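### The weights listed for the primary weighted kappa are the quadratic weights for four categories, but the itch item has five, so they contradict the method the protocol names

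*Protocol*

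**What the plan says.** Protocol, Analysis methods, Objective 1, describes the item as follows: "The itch question is an ordinal scale from 0 to 4 (ranging from no days to every day". Agreement between the two versions of the item "will be evaluated using both a weighted kappa (primary method) and kappa". On the weights it says "Kappa weightings will be applied using a quadratic approach as follows", and then lists four. Exact agreement scores 1.00, a one-point gap scores 0.89 and a two-point gap scores 0.56. The last entry reads "Difference of 3+ between the POEM and RECAP questions = 0.00".

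High agreement is then set at 0.8 or above, although the sentence calls the quantity a correlation. Objective 2 confirms the item range: "Using the original POEM scores (7-items, range from 0 to 28", so each item runs to 28 / 7 = 4. No reason is given for treating differences of 3 and 4 alike.

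**The concern.** A 0 to 4 item has five levels and a largest possible difference of 4. Quadratic weights should therefore reach zero at a difference of 4, but the listed ones reach it at 3. The text names one scheme and tabulates another.

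An analyst who enters the listed weights and one who uses a standard quadratic option over five levels would both be following the protocol, and would generally report different kappas. This is the primary agreement measure for whether the frequency question need be collected only once, and the results are meant to inform HOME recommendations. The protocol itself fixes the numbers, so this is not a detail left for a later analysis plan.

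**Working it through.** **Inputs from the protocol.** Item range 0 to 4, so k = 5; quadratic weighting; listed weights 1.00, 0.89, 0.56, 0.00 for differences d = 0, 1, 2, 3+.

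**Step 1: reproduce the listed weights.** Quadratic weights are w = 1 − (d/(k−1))².

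| d | k = 4: 1 − d²/9 | k = 5: 1 − d²/16 | Listed |
|---|---|---|---|
| 0 | 1.0000 | 1.0000 | 1.00 |
| 1 | 0.8889 | 0.9375 | 0.89 |
| 2 | 0.5556 | 0.7500 | 0.56 |
| 3 | 0.0000 | 0.4375 | 0.00 |
| 4 | – | 0.0000 | 0.00 |

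The list matches k = 4 to two decimals and does not match k = 5. Linear weights do not match either (k = 4: 1, 0.67, 0.33, 0; k = 5: 1, 0.75, 0.50, 0.25, 0).

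**Step 2: isolate what matters for kappa.** Let O and E be the observed and chance-expected mean squared differences, and o4 and e4 the observed and expected shares of pairs that differ by 4.

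- Five-category kappa = 1 − O/E. The divisor 16 cancels; so would 9.
- Listed scheme, before rounding: d = 4 counts as 9 instead of 16, so kappa = 1 − (O − 7·o4)/(E − 7·e4).

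The listed scheme gives the lower kappa exactly when o4/e4 < O/E. If nobody scores 0 on either item (or nobody scores 4), then o4 = e4 = 0 and the two agree. Rounding to 0.89 and 0.56 moved kappa by 0.0015 or less in the tables examined.

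**Step 3: size.** The protocol gives no response distribution, so the margins below are assumptions, applied to a bivariate normal cut into five levels.

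Uniform margins, latent correlation 0.85: E = 4.00, e4 = 0.08, O = 0.7986, o4 = 0.00013.

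- Five-category: 1 − 0.7986/4.00 = 0.800.
- Capped: 1 − (0.7986 − 0.0009)/(4.00 − 0.56) = 1 − 0.7977/3.44 = 0.768, or 0.769 with the rounded weights.

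| Assumed margins (levels 0 to 4, %) | Latent correlation | Five-category | Listed |
|---|---|---|---|
| 20/20/20/20/20 | 0.85 | 0.800 | 0.769 |
| 35/10/10/10/35 | 0.90 | 0.829 | 0.771 |
| 10/20/40/20/10 | 0.85 | 0.786 | 0.774 |
| 1/14/20/20/45 | 0.90 | 0.833 | 0.830 |

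The largest shift seen was 0.072 (the 35/10/10/10/35 margins at latent correlation 0.70: 0.595 against 0.523).

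**Step 4: a reversal.** Take 98% perfect agreement spread evenly over the levels and 2% of pairs at 0 versus 4, split equally. Each end level then has margin 0.98 × 0.2 + 0.01 = 0.206 and each middle level 0.196.

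- O = 0.02 × 16 = 0.32; E = 4.08; e4 = 2 × 0.206² = 0.0849.
- Five-category: 1 − 0.32/4.08 = 0.922.
- Capped: 1 − (0.32 − 0.14)/(4.08 − 0.594) = 1 − 0.18/3.486 = 0.948.

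Here the listed weights give the higher value.

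**Step 5: the 0.8 cut-off.** Take n = 281 (296 − 15, assuming that the 296 includes the excluded parent-completed records and that none are missing) and a true five-category kappa of 0.806. The simulated chance of an estimate of at least 0.8 is about 60% with five-category weights. With the listed weights it is about 15% (uniform margins), 40% (10/20/40/20/10) and 54% (1/14/20/20/45). At a true value of about 0.89 it is 100% under both schemes for these three margins.

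**The case against.** The wording 3+ explicitly covers a difference of 4, so a deliberate cap is possible. That stands as a possibility, but the text neither states nor justifies a cap, and it names a quadratic approach.

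A reader might infer that 0.89 and 0.56, being smaller than 0.9375 and 0.75, over-penalise small disagreements, so that kappa must come out too low. Step 2 does not support this: a constant rescaling of the penalties cancels, and only the 0-versus-4 penalty matters. Nor do the documents support a fixed downward bias. They give no response distribution, and Step 4 shows the opposite direction. Where very few people answer at one end of the scale, the shift is a few thousandths, well below the sampling error (standard deviation about 0.024 at n = 281 with 1% scoring 0).

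The stakes are also limited. The protocol calls the study exploratory, with no formal hypothesis test, and promises confidence intervals where appropriate. Unweighted kappa, the Pearson correlations and the re-run trial results do not use these weights. The items are described as identically worded, so agreement well above 0.8 is plausible, in which case the verdict would probably be unaffected. Applying the 0.8 cut-off to kappa is itself an inference from where the sentence stands, since it speaks of a correlation. All of this narrows the consequence; none of it reconciles the list with the scale.

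**Conclusion.** The point holds as an internal contradiction in the definition of the primary agreement statistic: a five-level item and a named quadratic method, with four-level weights. That part needs no assumptions.

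The numerical effect does rest on assumptions. Across the smooth distributions tried, the listed weights gave a kappa lower by about 0.003 to 0.07. The effect is nil apart from rounding if either end level is unused, and it reverses when 0-versus-4 pairs are over-represented. It can move the conclusion across 0.8 only when the true value is near 0.8. It should be corrected because it affects the primary statistic and costs almost nothing, not because a wrong conclusion is certain.

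**What to change.** Before kappa is computed, replace the four listed weights with 1.00, 0.9375, 0.75, 0.4375 and 0.00 for differences of 0, 1, 2, 3 and 4. Equivalently, name the software's standard quadratic option applied to all five levels. If capping the penalty at a difference of 3 was intended, say so, give the reason, and report the standard five-category quadratic kappa alongside.

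The cost is a few numbers in one list, with no new data and no extra analysis unless the cap is kept. Timing matters: changing the weights after the result is known would look driven by the result.

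### The Objective 1 rule for high agreement is set on a correlation of at least 0.8, although the planned primary statistic is weighted kappa

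*Protocol*

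**What the plan says.** Research question 1 is whether the two frequency items are "sufficiently similar to enable collection only once". The matching analysis is headed "Objective 1: To assess the level of agreement between the POEM and RECAP 'frequency of itch' questions" (Protocol, Analysis methods). Agreement there "will be evaluated using both a weighted kappa (primary method) and kappa", followed by a list of kappa weights. The rule that turns the result into a recommendation comes next: "A high level of agreement (suggesting that the item may not need to be asked twice) is defined as being a correlation" of at least 0.8.

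The same sentence appears again, word for word, under Objective 3, where associations "will be explored using Pearson's correlation coefficients and 95% confidence intervals". The Analysis row of the synopsis keeps the two kinds of statistic apart: "Levels of agreement calculated using weighted kappa and kappa statistic" and, separately, "Correlations reported using Pearson's correlation". The Data sources section also names kappa and correlation as two things. Nowhere is the 0.8 threshold attached to kappa, and no comparison of the mean or marginal scores of the two items is planned.

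**The concern.** The statistic in the decision rule is not the statistic the objective plans. Read literally, weighted kappa is primary but has no benchmark, while the benchmark belongs to a measure of association.

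The difference matters for this question. To collect the item once, one answer must be able to stand in for the other. A context or order effect could make respondents answer higher in one questionnaire than in the other. Kappa is lowered by such a shift; Pearson's r is not affected by a constant one. Objective 3 covers all available itch measurements, including both frequency items, so an r for this pair may well be on the table. Two analysts following the text could then apply 0.8 to different numbers and reach different conclusions, and the conclusion is meant to inform HOME consensus recommendations.

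**Working it through.** **Inputs from the protocol.** A five-category item scored 0 to 4; a threshold of 0.8; listed weights of 1.00, 0.89, 0.56 and 0.00 for differences of 0, 1, 2 and 3 or more. The 0.8 is a chosen cut-off with no stated derivation, so there is no figure to reproduce. The documents give no response distributions; every distribution below is an assumption.

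**Formula.** With five-category quadratic weights 1 − (d/4)², weighted kappa is

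κ = 2·r·s₁·s₂ / (s₁² + s₂² + b²) = 1 − E(d²) / (s₁² + s₂² + b²),

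where s₁ and s₂ are the item SDs, b is the mean difference and d the individual difference. The mean difference b lowers κ but does not appear in r. With equal SDs and b = 0, κ = r.

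**Case A: first item uniform on 0 to 3, everyone one category higher on the second.** s₁² = s₂² = 1.25, b = 1, r = 1. κ = 2.5 / (2.5 + 1) = 0.71.

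**Case B: 10/20/40/20/10%, with 75% of those below the ceiling shifted up one.** b = 0.75 × 0.90 = 0.675 and E(d²) = 0.675; s₁² = 1.20, s₂² = 1.119, covariance 1.05. r = 1.05 / √(1.20 × 1.119) = 0.91. κ = 1 − 0.675 / (1.20 + 1.119 + 0.456) = 0.76.

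**Case C: uniform on 0 to 4, everyone below the ceiling shifted up one.** b = 0.8 and E(d²) = 0.8; s₁² = 2, s₂² = 1.36. κ = 1 − 0.8 / (2 + 1.36 + 0.64) = 0.80.

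For comparison, the table also gives kappa with the protocol's listed weights.

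| First-item distribution | Share below ceiling shifted | Mean difference | Exact agreement | r | κ, five-category quadratic | κ, listed weights |
|---|---|---|---|---|---|---|
| Uniform 0–3 (A) | all | 1.00 | 0% | 1.000 | 0.714 | 0.675 |
| 10/20/40/20/10% (B) | 75% | 0.675 | 32.5% | 0.906 | 0.757 | 0.740 |
| Uniform 0–4 (C) | all | 0.80 | 20% | 0.970 | 0.800 | 0.769 |
| Uniform 0–4 | 75% | 0.60 | 40% | 0.939 | 0.850 | 0.827 |
| Uniform 0–4 | half | 0.40 | 60% | 0.938 | 0.900 | 0.884 |
| 10/20/40/20/10% | half | 0.45 | 55% | 0.899 | 0.830 | 0.819 |
| 5/15/20/20/40% | half | 0.30 | 70% | 0.932 | 0.899 | 0.891 |
| 2/13/20/20/45% | half | 0.275 | 72.5% | 0.924 | 0.889 | 0.885 |

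**Reading the table.** Every row passes a rule of r ≥ 0.8. A and B fail a kappa rule at 0.8. All the half-shift rows pass both rules. In these tables the shift is the only source of disagreement. If random disagreement has already brought r down to 0.85, the formula with a mean difference of 0.5 and equal SDs of 1.0 to 1.3 gives κ from 1.70 / 2.25 = 0.76 to 2.873 / 3.63 = 0.79. With a mean difference of 0.25 it gives 0.82 to 0.84, which passes.

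**Kappa is not a complete safeguard either.** In case C, κ is 0.80 although only 20% of answers match exactly. With the listed weights that case falls to 0.77, but the 75% row still passes (0.83) with a mean difference of 0.6 and 40% exact agreement.

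**Objective 2 as a back-stop.** It compares the between-group difference under two POEM scorings. A shift of the same mean size in both arms cancels from that difference, so Objective 2 would not reliably reveal it.

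**The case against.** The best reply is that the word is loose. The sentence follows directly on the kappa weights, speaks of agreement, and is identical to the one under Objective 3, which suggests copying. Weighted kappa is labelled the primary method, so many readers would apply 0.8 to it without hesitation. This stands as a reason to think the intention was sound. It does not settle the text, because the synopsis and the Data sources section treat kappa and correlation as different statistics.

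It is also fair that the disagreement between the rules needs a sizeable shift between near-identical questions, and that case A requires nobody to score 4 on the first item. Both kappas will be reported whichever word is used, and unweighted kappa reacts strongly: −0.23 in case A, and 0.41 to 0.59 in the half-shift rows. A careful reader of the results would have a warning.

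A reader might go further and infer that the rule is deficient because it does not require the lower confidence limit to reach 0.8. The protocol does not support that as an error. It describes an exploratory project that tests no hypothesis and will show 95% CIs where appropriate; a point-estimate benchmark with its interval beside it suits that purpose.

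**Conclusion.** The decision rule for research question 1 names the wrong statistic as written and should be corrected. The practical effect is conditional. Under assumed distributions, r passes and quadratic kappa fails when the shift is large (1.00 against 0.71; 0.91 against 0.76), while with half of those below the ceiling shifted both pass (r 0.90 to 0.94, kappa 0.83 to 0.90).

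Two stronger readings are tempting and not supported. One is that the investigators mean to judge agreement by Pearson's r; the protocol makes weighted kappa primary, so the wording shows a mismatch and not an intention. The other is that any systematic difference would be missed by r and caught by kappa; moderate shifts pass both rules, and kappa can reach 0.80 with a mean difference of 0.8. With kappa reported regardless and the project feeding later consensus work, this is a point to fix, not a fatal one.

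**What to change.** - Under Objective 1, replace the correlation threshold with weighted kappa of at least 0.8, presented with its 95% CI. Keep the correlation threshold under Objective 3 only.
- Report beside it the percentage of exact agreement and the mean RECAP minus POEM difference with 95% CI, so that a systematic shift is visible even when kappa passes.
- When the threshold is moved to kappa, reconcile the weights as well. The listed values equal 1 − (d/3)², the quadratic set for four categories; a five-category item gives 1.00, 0.94, 0.75, 0.44 and 0.00. This is a separate matter, but it changes the number to be compared with 0.8 (0.80 against 0.77 in case C).

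The cost is one phrase and two descriptive statistics from data already in hand. No new data are needed, and the status of the project as exploratory is unchanged.
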